8.2. Analysis of the secondary endpoint

- Absolute values and changes in hemoglobin level (g/L) after 4, 8, and 12 weeks of therapy (determined at the final visit) between the study groups.
- Changes in iron metabolism parameters mean values (ferritin, transferrin, percent transferrin saturation, serum iron) during the therapy period (from the screening to the study end visit) in the study groups.
- The responder rate (%) was determined as an increase in the hemoglobin level by ≥ 20 g/L after 12 weeks of treatment (from screening to the study end visit) in the study groups.

The data will be checked for compliance with the normal distribution law using the Shapiro-Wilk test.

Intergroup comparison of secondary endpoints related to quantitative scales will be performed using Student's t-test for independent samples if the data correspond to the normal distribution law; otherwise, the Mann–Whitney U test will be applied to independent samples.

Intergroup comparisons of secondary endpoints related to categorical scales will be performed using Pearson's chi-square test if the number of points in each cell of the crosstab is ≥ 5 , or Fisher's exact test if at least one of the crosstab cells contains < 5 points.

The dynamics will be assessed using ANOVA methods with repeated measurements if the data correspond to the normal distribution; otherwise, the Friedman test will be applied.

9. Safety analysis

Safety evaluation of the study therapy will be performed throughout the study and will be based on the detection of any adverse events occurring during the study. The following will be performed:

- Physical examination, including measurement of blood pressure and heart rate, and gastrointestinal disorders identification (at the screening, during the second visit, and the final visit).
- Complete blood count (at screening and in 4, 8, and 12 weeks of treatment);
- Blood biochemistry (at screening and after 12 weeks of treatment);
- Clinical urinalysis, pregnancy test (at screening and in 12 weeks);
- Registration of concomitant therapy (at each visit).

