## 4.4 Subjectivity minimization measures

#### 4.4.1 Randomization

A randomized open prospective comparative phase III trial in parallel groups with active control is planned.

Randomization is a measure aimed at minimizing subjectivity due to the random distribution of the patient. Randomization will exclude the subjective, including unconscious, selection by the researcher in one of the patient population groups, which will differ significantly from the population recruited in the second.

Automated randomization lists will be formed, randomization will be carried out through the e-CRF system with a randomization module.

Each randomized patient will be assigned a unique number for issuing the drug during the study. The patient's number consists of the letter R and the numbers from 001 to 336. The numbering of patients does not depend on the research center and is "transparent". In addition to the number, the system will indicate the treatment group to which the patient is distributed. Randomization will be stratified by two factors depends on patient's data (gender and baseline Hb level) entered to the e-CRF before randomization:

- Gender (male vs female);

- Hb level (80–94 g/L vs 95–110 g/L).

In order to randomize patients in the e-CRF system, each center will be provided with secure access and appropriate training in the use of the system will be provided.

The randomization number and name of the treatment group issued by the system. The researcher records in the primary documentation and enters information on the randomized patient in the list of included patients. The randomization number cannot be changed during the study.

The drug is given to the patient according to the information on the group of therapy received from e-CRF system. Research therapies also cannot be changed during the research process.

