#### 9.1.3 Analysis of the secondary effecacy endpoints

#### Secondary efficacy endpoints:

All secondary efficacy analysis will be considered explorative, therefore, no multiplicity correction will be done for any tests, and no formal power calculation will be provided for the test results.

• Absolute values and changes (compared to baseline) of blood hemoglobin level (g/L) after 12 weeks of treatment (during the final visit) between the study groups.

Values at individual time points and values of change between the individual time points will be compared using the t-test or Mann-Whitney test depending on the normality of the distribution (which will be tested using Shapiro-Wilk test).

Additionally, it is planned to use ANCOVA for analysis of changes in the assessed parameters over time where group will be a fixed factor, screening hemoglobin level will be a covariate, and hemoglobin level at Week 12 will be a response variable.

• Changes in average values of iron metabolism parameters (ferritin, transferrin, percent transferrin saturation, serum iron) during the treatment period (from screening till the final visit) in the study groups.

Values at individual time points (baseline and Week 12) and values of change between the individual time points (baseline and Week 12) will be compared using the t-test or Mann-Whitney test depending on the normality of the distribution (which will be tested using Shapiro-Wilk test).

• The percentage (%) of subjects with response to the therapy, determined as an increase in hemoglobin level by 20 g/L and more after 12-weeks of treatment (from screening till the final visit) in the study groups.

Comparison between the two groups will be performed using the Fisher's exact test or chi-square test depending on the number of expected observations per cell (<5 or  $\geq$ 5). Two-sided 95% confidence interval will be calculated using exact Clopper-Pearson method.

These changes will be compared between the groups using the t-test or Mann-Whitney test depending on the normality of the distribution (which will be tested using Shapiro-Wilk test).

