Appendix 1. Table layouts

PRIMARY ENDPOINT

Parameter	Coef.	Standard error	t -value	p -value	С	2I
Constant (intercept)						
Group R versus Group T						
Gender M versus F						
Weight						
Base hemoglobin factor (80–94 g/L compared to 95–110 g/L)						
Hemoglobin level at screening						
Interactions						

SECONDARY ENDPOINTS

Table 1. Hemoglobin, frequency analysis of the treatment efficacy after 12 weeks

Hemoglobin (g/L)					
Group	Parameter	Value			
	Total observations				
$R - Maltofer^{\mathbb{R}}$	Responders, n				
	Responders, %				
	95% CI				
	Total observations				
T – Ferrum Lek®	Responders, n				
	Responders, %				
	95% CI				
Group comparison	Pearson's chi-square test, p-value				

Table 2. Results of analysis of variance

Coefficients	Evaluation	Standard error	t-value	p-value
(Intercept)				
V1_CB_LBORRES_HB				
(Hemoglohin level at screening)				
Group T – Ferrum Lek [®]				
(Test to reference group factor)				

Table 3. Hemoglobin, absolute values, g/L

Hemoglobin (g/L)						
Group	Parameter	Screening	Week 4	Week 8	Week 12	
	Number of observations					
	Number of missing values					
	Mean value					
R – Maltofer®	95% CI					
	Standard deviation					
	Median					
	Minimum value					
	Maximum value					

	1st quartile		
	3rd quartile		
	Interquartile range		
	p-value (Shapiro–Wilk test)		
	Number of observations		
	Number of missing values		
	Mean value		
	95% CI		
	Standard deviation		
	Median		
T – Ferrum Lek [®]	Minimum value		
	Maximum value		
	1st quartile		
	3rd quartile		
	Interquartile range		
	p-value (Shapiro–Wilk test)		
Group	Criterion		
comparison	p-value		

SOP-05-02_RF01 Statistical Analysis Plan_01APR2020_3.0

Table 4. Hemoglobin, changes, g/L

Hemoglobin (g/L)						
Group	Parameter	Week 4 – Screening	Week 8 – Screening	Week 12 – Screening		
	Number of observations					
	Number of missing values					
	Mean value					
	95% CI					
	Standard deviation					
	Median					
R – Maltofer®	Minimum value					
	Maximum value					
	1st quartile					
	3rd quartile					
	Interquartile range					
	p-value (Shapiro–Wilk test)					
	Number of observations					
	Number of missing values					
	Mean value					
T − Ferrum Lek®	95% CI					
	Standard deviation					
	Median					
	Minimum value					

STATISTICAL ANALYSIS PLAN

	Maximum value		
	1st quartile		
	3rd quartile		
	Interquartile range		
	p-value (Shapiro–Wilk test)		
Group comparison	Criterion		
	p-value		

Table 5. Blood serum iron, absolute values, μ mol/L

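### Most secondary efficacy comparisons are unadjusted and end in a bare p-value: sex and Hb stratum are unused, and no between-arm difference with a CI is prespecified for Week 4 and 8 Hb, the iron parameters or responders

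*SAP*

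**What the plan says.** SAP 8.2 opens its rule for continuous secondary endpoints with "Intergroup comparison of secondary endpoints related to quantitative scales will be performed using" and then names an unadjusted two-sample test, chosen after a normality check: "Student's t-test for independent samples if the data correspond to the normal distribution law; otherwise, the Mann–Whitney U test will be applied". For responders (Hb rise of at least 20 g/L at Week 12) it reads "Intergroup comparisons of secondary endpoints related to categorical scales will be performed using Pearson's chi-square test", with Fisher's test when cell counts are small. For the time course it adds "The dynamics will be assessed using ANOVA methods with repeated measurements if the data correspond to the normal distribution", with the Friedman test otherwise. No covariate or stratum is named in that section.

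Protocol 9.1.3 gives the same tests and adds one model for Week 12 Hb, in which "screening hemoglobin level will be a covariate, and hemoglobin level at Week 12 will be a response variable". The SAP carries that model only as a layout, "Table 2. Results of analysis of variance", with rows for the intercept, screening Hb and the group coefficient, and columns for estimate, standard error, t and p. The text of SAP 8.2 does not mention it.

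For responders the protocol says "Two-sided 95% confidence interval will be calculated using exact Clopper-Pearson method", which is an interval for a single proportion. The SAP responder layout has n, % and 95% CI for each arm and one p-value for the comparison. Secondary Tables 3 to 12 (Hb and the four iron parameters) have per-arm means with 95% CIs, and comparison rows holding only the test used and its p-value.

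Protocol 4.4.1 says "Randomization will be stratified by two factors": sex, and Hb 80-94 versus 95-110 g/L. Both are in the primary ANCOVA (protocol 9.1.2, SAP 8.1). Protocol 9.1.3 declares all secondary efficacy analyses explorative.

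**The concern.** Two things are lost.

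The first is precision. Each iron parameter and Hb has a screening value, and sex and Hb stratum are known for everyone at randomisation. The primary analysis uses this information. The routine secondary comparisons use it only as far as a change score subtracts the baseline.

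The second matters more: interpretation. The trial asks whether the test product is worse by less than a set amount. A test of no difference that returns p above 0.05 does not answer that. A reader who wants to know how large a shortfall in responders, ferritin or early Hb response the data exclude needs a between-arm difference with its interval, and the planned output does not print one for these endpoints.

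**Working it through.** **Step 1: where each piece of information is used.**

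| Endpoint | Baseline used? | Sex and Hb stratum used? | Between-arm result |
|---|---|---|---|
| Week 12 Hb change (primary) | Yes, covariate | Yes | LS mean difference with CI |
| Week 12 Hb (secondary ANCOVA) | Yes, covariate | No | Group coefficient, SE, t, p |
| Hb at Weeks 4 and 8 | Only by subtraction in change scores | No | p-value only |
| Four iron parameters | Only by subtraction in change scores | No | p-value only |
| Responders | Only through the definition as a rise | No | p-value only |

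**Step 2: the plan's own sample size, to confirm the inputs.** Margin 5, SD 15, true difference 0 and 80% power, from protocol 9.3 and SAP 2.3. With n per arm = 2 × (15/5)² × (z_α + z_β)²:
- one-sided 0.025: 18 × (1.960 + 0.842)² = 141.3, so 142
- one-sided 0.0245, the plan's final-look level: 18 × (1.969 + 0.842)² = 142.2, so 143

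The stated 143 completers per arm reproduces. No secondary endpoint was sized; 143 and SD 15 are borrowed below for scale, and using them at Weeks 4 and 8 assumes the same SD holds there.

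**Step 3: precision of the Hb change.** Unadjusted 95% half-width = 1.96 × 15 × √(2/143) = 3.48 g/L. Adjustment multiplies it by √(1 − r²), where r is the correlation of baseline with change. The documents give no r, so these values are assumptions:

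| r | Variance reduction | Half-width (g/L) | Equivalent unadjusted n per arm |
|---|---|---|---|
| 0.2 | 4% | 3.41 | 143/0.96 = 149 |
| 0.3 | 9% | 3.32 | 143/0.91 = 157 |
| 0.5 | 25% | 3.01 | 143/0.75 = 191 |

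**Step 4: absolute values and changes together.** SAP 8.2 tests both. Assume screening Hb is uniform on 80-110 g/L (SD 30/√12 = 8.7), SD of change is 15, and follow-up Hb has slope b on baseline. Half-widths in g/L:
- b = 0: change 3.48, absolute 2.84, ANCOVA 2.84
- b = 0.5: change 3.48, absolute 3.48, ANCOVA 3.33
- b = 1: change 3.48, absolute 4.01, ANCOVA 3.48

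ANCOVA matches or beats both at each slope. Its advantage over the better of the two is small or nil.

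**Step 5: what the responder table would not show.** Under a normal model with the plan's mean rise of 8-15 g/L and SD 15, the responder rate is 1 − Φ((20 − 8)/15) = 21% to 1 − Φ((20 − 15)/15) = 37%. The half-width of an unadjusted risk difference is 1.96 × √(2p(1 − p)/143):
- p = 0.212: 9.5 percentage points
- p = 0.369: 11.2 percentage points

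An observed deficit of 9 points would then have a 95% interval reaching 9 + 9.5 = 18.5 to 9 + 11.2 = 20.2 points, while giving p above 0.05. The layout would print only that p-value beside two separate per-arm intervals.

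**Step 6: adjustment for responders.** Illustrative simulations at 143 per arm compared chi-square with logistic regression on baseline Hb:
- True difference 5 g/L (1,000 runs): power 56% against 68% at b = 0 (r = −0.58), and 58% against 60% at b = 0.5 (r = −0.29).
- True difference 6 g/L (1,500 runs): 68.5% against 68.5% at |r| = 0.2, and 67.3% against 74.1% at |r| = 0.5.

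These are powers to detect a difference, under differences the plan does not expect. They show only that the efficiency gain runs from nothing to moderate.

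**The case against.** The strongest defence has four parts.

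- **Baseline is not ignored.** A reader of SAP 8.2 alone might infer that it is. The documents do not support that: Week 12 Hb has its ANCOVA and layout, change scores use baseline in part, and protocol 9.1.1 and SAP 5 add adjusted analyses when a baseline variable differs significantly between arms. This stands, except that the last provision is triggered by the data and so is not a prespecified adjusted estimate.
- **Between-arm estimates are not wholly absent.** A reader might infer that no secondary endpoint has one. Secondary Table 2 gives a group coefficient with SE for Week 12 Hb, from which a CI follows. For the rest, unadjusted differences can be worked out from the per-arm summaries, so it goes too far to say the secondary endpoints can neither support nor contradict the primary result. This also stands. What cannot be recovered from the tables is an adjusted or stratified difference.
- **The analyses are explorative and unpowered.** True, and they do not enter the primary non-inferiority decision. They are not without consequence, though: protocol 9.2 and SAP 11 let the sponsor consider interim results on primary and secondary endpoints when deciding whether to stop.
- **The size of the gain is assumed.** True. Eligibility restricts screening Hb to between 80 and 110 g/L and ferritin to below 30 µg/L, which may hold the correlations down, and nothing in the documents supports a particular r for the iron parameters.

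**Conclusion.** The point holds in a limited form. Sex and Hb stratum enter no routine secondary analysis. For Hb at Weeks 4 and 8, the iron parameters and responders there is neither a prespecified baseline-adjusted model nor a between-arm difference with a CI. The Week 12 Hb model exists in the protocol and in a SAP layout, but it is missing from the text of SAP 8.2 and omits sex and stratum.

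The missing effect estimates are the firmer half, because they rest on the layouts alone. The precision half is sure in direction but not in size: 4-25% of variance for an assumed r of 0.2 to 0.5, and possibly negligible, including for responders at low r. A reader might go further and infer bias or an inflated error rate. Nothing in the plan supports that: unadjusted tests after stratified randomisation remain valid, and the primary conclusion is untouched. The change is worth making because it is free, not because the present analyses are wrong.

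**What to change.** - Write the protocol's Week 12 Hb ANCOVA into SAP 8.2.
- Extend it to each continuous secondary endpoint and visit, with treatment, that parameter's own screening value, sex and Hb stratum. Report the LS mean difference with 95% CI. Fix the scale for each parameter in advance, since the rank-test fallback would no longer be the main comparison.
- For responders, report a between-arm difference with 95% CI, either stratified over the four sex by Hb-stratum cells (for example a Mantel-Haenszel risk difference) or adjusted for baseline Hb and sex.
- Add a difference-with-CI row to the responder table and to secondary Tables 3 to 12, and a CI column to secondary Table 2.
- Keep the unadjusted per-arm summaries as descriptive.

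The cost is SAP wording, table layouts and programming. No new data, visits or patients are needed.

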#### Safety Measurements

Safety evaluation will include:

1) Determination of the total number, frequency and severity of:

- I. adverse events (AEs) irrespective of their relation to treatment;
- II. AEs related or possibly related to the treatment received;
- III. AEs requiring termination of the therapy.

2) Complaints on digestive system disorders (defined through MedDRA SMQ for the corresponding symptoms), considered as related to the study therapy by the investigator, will be analyzed separately.

Descriptive statistics will be used for presentation of the result. Comparison of all AE incidence between the study groups will be performed using the Fisher's exact test or chi-square test depending on the number of expected observations per cell (<5 or  $\geq 5$ ), and comparison of intensity (and possible causal relationship between the treatment received and the AE) will be performed using Cochrane-Armitage trend test for the ordered categorical data.

3) Changes in laboratory test results (assessed in central laboratory) over time and frequency of abnormal test results (according to the normal ranges of central laboratory) will be summarized by group and also compared by group using corresponding tests for quantitative data and qualitative data (see below).

4) Changes in vital signs over time and frequency of abnormal physical examination findings will be summarized by group and also compared by group using corresponding tests for quantitative data and qualitative data (see below).

Quantitative data will be compared using the t-test or Mann-Whitney test depending on the normality of the distribution (which will be tested using Shapiro-Wilk test).

Qualitative data will be compared using the Fisher's exact test or chi-square test depending on the number of expected observations per cell (<5 or  $\geq 5$ ).

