#### 9.1.4 Safety parameteres analysis

Safety evaluation will include:

- 1) determination of the total number, incidence and severity of the folowing:
  - I. adverse events (AEs), regardless of their relationship to the treatment;
  - II. AEs associated or potentially associated with the drug;
  - III. AEs leading to discontinuation.

2) Gastrointestinal disorders (determined by means of a standardized MedDRA query for the corresponding symptoms), regarded by the Investigator as related to the study therapy, will be analyzed separately.

Methods of descriptive statistics will be used to represent the results. A comparison of the incidence of new AE cases in the study groups will be performed using the Fisher's exact test or

the chi-square test, depending on the number of proposed observations in one cell (<5 or  $\ge 5$ ), and a comparison of the severity (and the possible causality between the study drug and AE) will be conducted using the Cochran—Armitage test for linear trends for ordered categorical data.

3) Changes in the results of laboratory studies (conducted in the central laboratory) over time and the incidence of abnormal results of studies (based on the reference values of the central laboratory) will be summarized by group, and a comparison will be made between the groups using appropriate tests for quantitative and qualitative data (see below).

4) Changes in the vital signs over time and the incidence of pathological abnormalities revealed during physical examination will be summarized by group, and a comparison will be made between the groups using appropriate tests for quantitative and qualitative data (see below).

Comparison of quantitative data will be conducted using the t-test or the Mann—Whitney test, depending on the distribution normality (which will be estimated using the Shapiro—Wilk test).

Qualitative data will be compared using the exact Fisher's exact test or the chi-square test, depending on the number of proposed observations in one cell (<5 or  $\geq 5$ ).

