9.1. Adverse events

The safety assessment will include determining the total number, frequency, and severity of:

- 1. Adverse events (AEs), regardless of their relation to the treatment;
- 2. AEs associated or potentially associated with the medicinal product;
- 3. AEs requiring treatment discontinuation.

Adverse events will be coded using the MedDRA nomenclature in the latest version. These will be represented by the preferred term (PT) and systemic organ class (SOC).

Methods of descriptive statistics will be used to represent the results. Comparison of the incidence of new cases of AE in the study groups will be carried out using Fisher's exact test or Pearson's χ^2 test, depending on the number of observations in one cell (< 5 or \geq 5).

Changes in the results of laboratory tests over time and the incidence of abnormal test results (based on the reference values of the central laboratory) will be summarized by groups, and a comparison will be made between the groups using appropriate tests for quantitative and qualitative data.

Safety data will be analyzed using the methods designated for the application of efficacy data evaluation.

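### The SAP chooses Fisher or chi-square by observed cell counts where the protocol uses expected counts, and its table shells follow neither rule

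*SAP*

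**What the plan says.** **Protocol.** The Synopsis, 4.1 (Safety Measurements) and 9.1.3 choose between Fisher's exact test and chi-square "depending on the number of expected observations per cell", with the cut at 5. Section 4.1 applies this to AE incidence and to qualitative safety data; 9.1.3 applies it to the responder rate. Section 9.1.4, on AEs, has "depending on the number of proposed observations in one cell", where the odd adjective looks like a translation of expected.

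**SAP text.** Section 8.2 uses "Pearson's chi-square test if the number of points in each cell of the crosstab is" at least 5, and "Fisher's exact test if at least one of the crosstab cells contains < 5 points". These are counts in the table itself, that is, observed counts. Section 9.1 chooses the AE test "depending on the number of observations in one cell", again with the cut at 5, and adds: "Safety data will be analyzed using the methods designated for the application of efficacy data evaluation".

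**SAP shells (Appendix 1).** The AE tables have one p-value column, labelled for Fisher's test, for every row. The responder table (Secondary Endpoints, Table 1) has one p-value line, labelled for Pearson's chi-square.

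SAP section 1 says that the analysis conforms to the protocol. Protocol 9.7 asks that departures from the statistical plan be described and justified. The SAP gives no reason for the change.

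**The concern.** Expected counts depend only on the table margins: arm sizes and total events. Observed counts depend on how the events split between arms. Under the SAP rule the observed difference therefore helps to choose the test, and it can choose only the more conservative one.

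Safety is the trial's stated secondary objective, and AEs are tabulated by system organ class and preferred term. The reference product's side-effect table (Protocol 2.1.2) puts diarrhea, nausea and indigestion between 1/100 and 1/10, which is where small cells arise. In a trial meant to show that two products are alike, lost sensitivity leans toward finding no difference. Three conflicting specifications of one test also leave room to choose after the data are seen.

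**Working it through.** **1. Arm size.** Inputs from SAP 2.3: margin 5 g/L, SD 15 g/L, power 80%, 143 completers and 168 randomised per arm. The fixed-sample formula at one-sided 0.025 gives n = 2 × (1.960 + 0.842)² × 15²/5² = 141.3, so 142; at the final-look level of 0.0245 it gives 143. Then 143/0.85 = 168.2. The stated sizes reproduce, so 143 and 168 per arm are used below.

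**2. Where the rules part.** With equal arms the expected event count per arm is (total events)/2.
- Protocol rule: Fisher if total/2 < 5, that is, fewer than 10 events.
- SAP 8.2 rule: Fisher if either arm has 0 to 4 events.
- They differ only when total events are at least 10 and one arm has 0 to 4. If both arms have 5 or more, the total is at least 10, so the SAP rule never chooses chi-square where the protocol chooses Fisher. (A mirror image holds for non-events when nearly everyone has the event.)

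**3. Verdicts that change.** All 2×2 tables were enumerated, comparing uncorrected Pearson with two-sided Fisher at 0.05 (SAP 3.1). Only these splits, in either direction, change verdict:

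| Events | Pearson, 143/arm | Fisher, 143/arm | Pearson, 168/arm | Fisher, 168/arm |
|---|---|---|---|---|
| 2 v 9 | 0.031 | 0.060 | 0.032 | 0.061 |
| 3 v 10 | 0.047 | 0.085 | 0.048 | 0.086 |
| 3 v 11 | 0.028 | 0.051 | 0.029 | 0.052 |
| 4 v 12 | 0.040 | 0.069 | 0.040 | 0.070 |

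Larger imbalances (2 v 10, 3 v 12, 4 v 13 and beyond) are significant under both rules. With a continuity-corrected chi-square, no verdict changes.

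**4. Power.** The documents give no planning rates for AEs, so the rates here are assumptions. Method: exact binomial enumeration, 168 per arm, two-sided 0.05.

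| True rates | Protocol rule | SAP text rule | Fisher always (shell) |
|---|---|---|---|
| 1% v 5% | 52.9% | 46.1% | 46.1% |
| 2% v 6% | 46.2% | 36.3% | 35.4% |
| 2% v 8% | 74.3% | 67.4% | 65.0% |
| 3% v 8% | 52.6% | 47.8% | 43.2% |
| 3% v 10% | 76.1% | 74.3% | 68.9% |
| 5% v 10% | 41.4% | 41.1% | 33.4% |
| 10% v 20% | 73.8% | 73.8% | 69.0% |
| 23% v 33% | 53.3% | 53.3% | 48.7% |

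The largest loss from the SAP text rule on the grid searched is about 10 points (1.8% v 6%: 51.0% to 40.9%). At 143 per arm, 2% v 7% goes from 52.7% to 42.5%, and 5% v 10% from 35.2% to 33.7%. Fisher throughout, as the AE shells are drawn, also costs about 5 to 8 points in the last three rows.

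**5. Size at 168 per arm (protocol rule v SAP text rule).** Equal true rates of 3%: 3.5% v 2.0%. Of 4%: 4.6% v 2.5%. Of 5%: 4.8% v 3.3%. Of 10%: 5.2% under both. The maximum on the grid is 5.16% under either rule. With equal true rates of 3% and 4% the rules pick different tests in 23% and 22% of trials.

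**6. Responder rate.** Response is a rise of at least 20 g/L. Under a normal approximation with mean rise 8 to 15 g/L and SD 15 (SAP 2.3): z = (20 − 8)/15 = 0.80 gives 21%, and z = (20 − 15)/15 = 0.33 gives 37%. That is about 30 to 53 of 143 per arm, so both rules select chi-square.

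**The case against.** The case for leaving this alone has four parts.

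- **Scope.** The explicit observed-count sentence is in 8.2, where the only categorical endpoint is the responder rate, and there it changes nothing. This stands.
- **Wording.** SAP 9.1 does not say observed. It may be the protocol's 9.1.4 phrase with one word lost. That is possible, but the closing sentence of 9.1 carries the efficacy methods into safety, and 8.2 is unambiguous, so the text as written points to observed counts.
- **Shells.** As the AE tables are drawn, Fisher is reported on every row and the switching wording never decides the test. This is fair, but it adds a third specification and does not resolve the first two.
- **Consequence.** Fisher is valid, AE results are presented descriptively, and there is no AE power target, multiplicity control or decision rule. The protocol calls its secondary efficacy analyses exploratory, and 4.1 lists AE frequency among those endpoints. The chi-square version is unstated, and with a continuity correction the difference disappears. All of this stands and limits the weight of the point.

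A reader might infer that the SAP turns to Fisher exactly when the arms truly differ. It does not: the trigger is a cell of 0 to 4 with at least 10 events in total, which is frequent with equal true rates of 3% to 4%. A reader might also infer that real AE differences will generally be missed, or that the two documents generally give opposite significance for the same table. Only four borderline splits do so, and clear imbalances are significant either way.

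**Conclusion.** The SAP departs from the protocol without explanation, and its shells agree with neither text. The AE test is specified three ways: a switch on expected counts, a switch on observed counts, and Fisher throughout.

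The effect is limited. Four splits change verdict at 143 and at 168 per arm. The power loss from the observed-count switch is about 2 to 10 points when the lower arm's true rate is about 1% to 3%, and at most 1.5 points at the rates tried with a lower rate of 5% or more. The switch does not inflate type I error, and the responder analysis is practically unaffected. These figures rest on equal arms, uncorrected Pearson, and assumed AE rates. The material does not support a general bias toward a finding of no safety difference; it supports harmonising the rule before analysis.

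**What to change.** In SAP 8.2 and 9.1, restore the protocol's rule: Pearson's chi-square without continuity correction when every expected count is at least 5, and Fisher's exact test otherwise. Naming the uncorrected version is an addition, since neither document says which is meant. In Appendix 1, relabel the p-value columns of the AE tables and the p-value line of the responder table so that they report whichever test the rule selects.

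The cost is a few words in two sections plus the shell labels. With the restored rule, size stays below 5% for equal rates up to 6% in the cases run and peaks at 5.16% near equal rates of 10%, where the SAP rule gives the same figure.
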